4.2. Recruitment

Subjects will be recruited at each study site. The information collected at that time is used simply to rule out any obvious exclusion criteria, such as age and substance abuse/medical history, as well as to collect some simple demographic information. If a participant is deemed ineligible or decides not to participate in the study, their information is destroyed, i.e., shredded. If an individual appears to meet enrollment criteria and is interested in participating, a face-to-face interview is conducted by one of the project investigators. A release of information is obtained for review of any available historical and clinical data. The nature of the project, procedures, relative risks and benefits. and alternatives to participation in the project are discussed with the individual. Following this discussion, the individual is given a copy of the consent form to review, and any questions are answered. The process of informed consent will be obtained in accordance with 21CFR50 and local IRB standards by study personnel who have participated in institutionally approved training in human subject protection. Upon obtaining voluntary, written, informed consent, medical and psychiatric screening procedures will be used to confirm study eligibility. Documentation regarding the informed consent process and the subject's study participation will be made in the subject's medical record and/or study source documents.

In order to ensure a high rate of enrollment in the proposed study a number of procedures will be implemented under the direction of the Contract PI [name] and implemented via the weekly Coordinating Committee (CC) meetings that include all of the Site PIs, the DCRI Project Leader, and the Leader of the Assessment/Signal Detection Core for the study, [name]. As part of this effort, each site will submit a site recruitment plan which will be reviewed by the CC prior to the commencement of the trial. The Committee will discuss each plan and make suggestions for ways to facilitate recruitment at each site. Throughout the trial it will be the responsibility of [name] or his designee, to track recruitment closely at each site and to present these data at the regular CC meetings for review. This review will include discussing the recruitment at each site in the context of the recruitment strategies they are employing in order to make ongoing modifications of the recruitment strategies of slower recruiting sites. This will also provide a forum for PIs of sites that are more successful in recruiting to share the strategies that have been most effective with the PIs of slower recruiting sites. In general, we will attempt to optimize recruitment and retention by promoting practices that are associated with effective recruitment across the sites and minimize practices which are unsuccessful through careful planning, establishing input and PI and site staff buy-in, adaptive recruitment strategies to address site idiosyncrasies, and adopting comprehensive and active community outreach. Assessment of recruitment will be based on the rate of enrollment needed to meet our enrollment target. This target requires us to enroll 90 subjects in 9 months with 6 sites. As a result, each site will have to enroll 1.7 subjects per month for us to successfully meet our recruitment goal. Because it is understood that sites will vary in startup speed it is assumed that some sites will have to enroll more rapidly than 1.7 subjects per month for us to meet our recruitment target. As a result, we will assess sites against a benchmark of enrolling 2 subjects per month. All sites who do not meet this benchmark for more than 1 month and all sites that fall below 1.0 subject per month in any month will be the focus of a recruitment evaluation which

will result in the formation of a recruitment plan for that site which will be followed up with ongoing close monitoring. In the case where a site falls below a recruitment rate of one subject per month for 3 months a thorough evaluation of the site and the factors that might be responsible for the under-recruiting of subjects will be carried out. Such sites will be discussed with the NIMH Contracting Officer's Representative (COR) and considered for being dropped from the study. In this case the DCRI, in coordination with the NIMH COR, will need to determine what steps should be taken including assessing the wisdom of closing a low enrolling site and initiate a new one. Likewise, we will discuss with NIMH COR the need to add additional sites, if that proves necessary.

It is anticipated that we will enroll twice as many women as men mirroring the gender distribution of mood and anxiety spectrum disorders. Because we have geographically diverse sites, we anticipate that the study population will have the ethnic distribution of the general U.S. population. A strong effort will be made to achieve these racial/ethnicity distribution enrollment targets. Each site has experience recruiting minorities through a concentrated effort in communities that have high representation of ethnic and racial minorities and through advertisements in newspapers and radio stations whose readers/listeners are predominantly of specific racial or ethnic minorities. The CC will monitor the gender and racial/ethnic composition of the subjects enrolled throughout the study to assess whether the planned targets are being met. If not, the CC will work together to formulate a plan to address identified problems.

4.3. Screening

Screening Visit: Day -30 to Day -1 (4 - 6 hours)

Once a subject has signed an inform consent for this study subjects will undergo a set of screening tests to determine if they meet the inclusion/exclusion criteria for the study. These screening tests will include:

- Medical, psychiatric, and medication history
- Vital signs (temperature, blood pressure, and pulse)
- Physical examination
- Pregnancy Test (beta-HCG serum pregnancy test females only)
- Electrocardiogram (ECG)
- Urine drug screen
- Mini-International Neuropsychiatric Interview (MINI)
- Snaith-Hamilton Pleasure Scale (SHAPS)
- Temporal Experience of Pleasure Scale (TEPS)
- Visual Analogue Scale for Anhedonia (VAS)
- Columbia Suicide Severity Rating Scale (CSSRS)
- Clinical Global Impression Severity (CGI-S)
- Battery of clinical laboratory tests including: Complete blood count with differential, Electrolytes, Metabolic Panel, Thyroid Function Tests, Urinalysis
- Mock MRI scanning session

Those who qualify to continue with the study based on the screening assessment will be asked to return 1-30 days later for additional evaluations. Subjects who require medication tapering will discuss a medication tapering plan with a study physician during

this visit (for details see Section 4.1. Study Overview). This plan will be designed so that subjects are free of all excluded medications at least 5 half-lives prior to the baseline visit (see Section 3.3. Exclusion Criteria). Qualifying subjects will be instructed about not using any prohibited medications during the study including substances of abuse. They will be specifically instructed about not using Salvia divinorum, which has kappa opioid agonist effects and is not an illegal substance.

A potential subject who previously screen failed due to a positive breath test ONLY may be brought back for re-screening. Subject should sign a new informed consent and all screening procedures must be repeated.

4.4. Study Procedures

Baseline: Day 0 Visit (6 – 8 hours):

Following rigorous screening, subjects will return to the clinic/research unit up to 30 days later and undergo the following assessments and procedures:

- Structural MRI, fMRI during Monetary Incentive Delay Task, Resting State Connectivity fMRI
- Interval history
- Battery of clinical laboratory tests including: Complete blood count with differential, Electrolytes, Metabolic Panel, Thyroid Function Tests, Urinalysis.
- EEG
- Vital signs (temperature, blood pressure, and pulse)
- Physical examination
- Electrocardiogram (ECG)
- Snaith-Hamilton Pleasure Scale (SHAPS)
- Temporal Experience of Pleasure Scale (TEPS)
- Visual Analogue Scale for Anhedonia (VAS)
- Columbia Suicide Severity Rating Scale (CSSRS)
- Probabilistic Rewards Task (PRT)
- Effort Expenditure for Rewards Task (EEfRT)
- Hamilton Depression Rating Scale (HAM-D)
- Hamilton Anxiety Rating Scale (HAM-A)
- The Cognitive and Physical Functioning Questionnaire (CPFQ)
- Clinical Global Impression Severity (CGI-S)
- Clinical Global Impression Improvement (CGI-I)
- Adverse events assessment with the Patient Reported Inventory of Side-Effects (PRISE)
- Blood sample collection for tests for assessment for gastric adverse events including gastrin, and pepsinogen I/II levels.
- Blood sample collection to be sent to Rutgers for potential genetic analysis or other future analysis (optional)

At the end of this visit subjects will be randomized to CERC-501 10 mg or placebo, will be provided with enough study medication for a 2-week period and will be instructed to take the medication every morning. Subjects will also be instructed to bring all of their study drug packaging and unused study drug with them to each visit.

Week 1 – Telephone Follow Up:

Subjects will be called after one week to assess for any safety concerns. Any safety issues identified will be addressed as appropriate.

Week 2 Visits (4 – 6 hours per visit): +/- 4 days

At this visit subjects will undergo the following assessments and procedures:

- Interval history
- Battery of clinical laboratory tests including: Complete blood count with differential, Electrolytes, Metabolic Panel, Thyroid Function Tests, Urinalysis
- Vital signs (temperature, blood pressure, and pulse)
- Physical examination
- Electrocardiogram (ECG)
- Snaith-Hamilton Pleasure Scale (SHAPS)
- Temporal Experience of Pleasure Scale (TEPS)
- Visual Analogue Scale for Anhedonia (VAS)
- Columbia Suicide Severity Rating Scale (CSSRS)
- Clinical Global Impression Severity (CGI-S)
- Clinical Global Impression Improvement (CGI-I)
- Adverse events assessment with the Patient Reported Inventory of Side-Effects (PRISE)
- Inspection of medication blister packs to assess medication adherence
- Blood sample for drug blood level testing

At the end of this visit subjects will receive enough study medication for another 2 week period, and will be instructed to take the medication each morning, to bring all study drug packing and unused study drug to the next visit, and to return to the clinic/research unit in 2 weeks.

Week 4 Visit (4 – 6 Hours): +/- 4 days

At this visit subjects will undergo the following assessments and procedures:

- Interval history
- Battery of clinical laboratory tests including: Complete blood count with differential, Electrolytes, Metabolic Panel, Thyroid Function Tests, Urinalysis.
- Vital signs (temperature, blood pressure, and pulse)
- Physical examination
- Electrocardiogram (ECG)
- Snaith-Hamilton Pleasure Scale (SHAPS)
- Temporal Experience of Pleasure Scale (TEPS)
- Visual Analogue Scale for Anhedonia (VAS)
- Columbia Suicide Severity Rating Scale (CSSRS)
- Inspection of medication blister packs to assess medication adherence
- Blood sample for drug blood level testing
- Clinical Global Impression Severity (CGI-S)
- Clinical Global Impression Improvement (CGI-I)

- Adverse events assessment with the Patient Reported Inventory of Side-Effects (PRISE)
- Blood sample for tests for assessment for gastric adverse events including gastrin, and pepsinogen I/II levels.

At the end of this visit subjects will receive enough study medication for another 2 week period, and will be instructed to take the medication each morning, to bring all study drug packing and unused study drug to the next visit, and to return to the clinic/research unit in 2 weeks.

Week 6 Visit (4 – 6 Hours): +/- 4 days

At this visit subjects will undergo the following assessments and procedures:

- Interval history
- Battery of clinical laboratory tests including: Complete blood count with differential, Electrolytes, Metabolic Panel, Thyroid Function Tests, Urinalysis.
- Vital signs (temperature, blood pressure, and pulse)
- Physical examination
- Electrocardiogram (ECG)
- Snaith-Hamilton Pleasure Scale (SHAPS)
- Temporal Experience of Pleasure Scale (TEPS)
- Visual Analogue Scale for Anhedonia (VAS)
- Columbia Suicide Severity Rating Scale (CSSRS)
- Inspection of medication blister packs to assess medication adherence
- Blood sample for drug blood level testing
- Clinical Global Impression Severity (CGI-S)
- Clinical Global Impression Improvement (CGI-I)
- Adverse events assessment with the Patient Reported Inventory of Side-Effects (PRISE)

At the end of this visit subjects will receive enough study medication for another 2 week period, and will be instructed to take the medication each morning, to bring all study drug packing and unused study drug to the next visit, and to return to the clinic/research unit in 2 weeks.

Week 8 Visit (6 – 8 Hours): +/-4 days

At this visit subjects will undergo the following assessments and procedures:

- Structural MRI, fMRI during Monetary Incentive Delay Task, Resting State Connectivity fMRI
- Interval history
- Battery of clinical laboratory tests including: Complete blood count with differential, Electrolytes, Metabolic Panel, Thyroid Function Tests, Urinalysis
- Electroencephalogram (EEG)
- Vital signs (temperature, blood pressure, and pulse)
- Physical examination
- Electrocardiogram (ECG)
- Snaith-Hamilton Pleasure Scale (SHAPS)

- Temporal Experience of Pleasure Scale (TEPS)
- Visual Analogue Scale for Anhedonia (VAS)
- Columbia Suicide Severity Rating Scale (CSSRS)
- Probabilistic Rewards Task (PRT)
- Effort Expenditure for Rewards Task (EEfRT)
- Hamilton Depression Rating Scale (HAM-D)
- Hamilton Anxiety Rating Scale (HAM-A)
- The Cognitive and Physical Functioning Questionnaire (CPFQ)
- Blood sample collection to be sent to Rutgers for potential genetic analysis or other future analysis (optional)
- Clinical Global Impression Severity (CGI-S)
- Clinical Global Impression Improvement (CGI-I)
- Blood sample for tests for assessment for gastric adverse events including gastrin and pepsinogen I/II levels.
- Adverse events assessment with the Patient Reported Inventory of Side-Effects (PRISE)
- Inspection of medication blister packs to assess medication adherence
- Blood sample for drug blood level testing

At the end of this visit study drug will be discontinued and subjects will be instructed to return to the clinic/research unit in 4 weeks.

Week 12 Visit: Post Medication Follow-up (2 - 4 hours) +/- 4 days

At this visit subjects will undergo the following assessments:

- Vital signs
- Interval history
- Snaith-Hamilton Pleasure Scale (SHAPS)
- Temporal Experience of Pleasure Scale (TEPS)
- Visual Analogue Scale for Anhedonia (VAS)
- Columbia Suicide Severity Rating Scale (CSSRS)
- Adverse events assessment with the Patient Reported Inventory of Side-Effects (PRISE)
- Clinical Global Impression Severity (CGI-S)
- Clinical Global Impression Improvement (CGI-I)

At the conclusion of this visit subject participation in the study will end.

4.5. End of Participation / Early Termination

At the end of the week 12 visit, participation in the study will end. The results of all of the laboratory assessments and EEGs, ECGs, and physical examinations that could affect the subject's health care will be shared with them and their health care provider if they would like this to occur. Subjects will meet with the study physician and options for treatment will be reviewed. Participants will not be informed as to their treatment assignment at this meeting.

In case a subject is lost-to-follow-up, every possible effort must be made by the study site

personnel to contact the subject and determine the reason for withdrawal. The measures taken to follow up must be documented.

Subjects have the right to withdraw from the study at any time for any reason. If a subject withdraws from the study before Week 8, the subject should have a complete evaluation performed at the time of withdrawal that includes all Week 8 procedures **EXCEPT fMRI** (see Table 3 Schedule of Assessments). Subjects will be followed through Week 12 follow up unless they specifically withdraw their consent for further contact or for medical records review. When a subject withdraws before completing the study, the reason for withdrawal is to be documented on the eCRF and in the source document. Subjects who withdraw will not be replaced.

5. STORAGE OF DATA AND SAMPLES

After the database is closed, data will be stored in the secure server located at North Pavilion Datacenter, [name]. The server is named GNEISS. The data will stored in \\gneiss\ct. All data will be stored as SAS version 9 datasets. The software is maintained and managed by the Duke Clinical Research Institute (DCRI) Information Technology (IT) group. The Director of Statistical Operations is responsible for granting access to the database as per our Standard Operating Procedures (SOPs). Once a year, the Director of Statistical Operations or Associate Director of Statistics reviews all trial access permissions and remove any trial access that is no longer appropriate. The data will be stored in gneiss for a maximum of 6 years. After six years, it will be archived. The Director of Statistical Operations, the Associate Director, Statistical Group for Manuscript Analysis (SIGMA) & Faculty and Fellows Affairs, and the Lead Biostatistician for the study or designee will approve the archival of the files from the DCRI network. The final datasets will be stripped of identifiers prior to release for sharing.

Blood samples for mailing to Rutgers for storage for potential genetic or other future analyses will be collected at baseline and after 8 weeks of treatment with study drug. These samples will be handled, processed, and mailed in accordance with applicable state, federal, and international regulations.

All samples will be logged into protected computer databases with all coded identifiers received from the FAST-MAS sites. A unique in-house RU ID # will be assigned as samples are logged into the RUCDRLIMS. This RU ID # for each specimen will be used to track the sample throughout processing, transformation and DNA and Plasma extraction. This new ID # that is unrelated to sample origin provides an additional level of security for maintaining sample anonymity. The FAST-MAS ID # and RU ID # will be cross-referenced in the computer database. The Alternate ID # will not be entered into the clinical or genetic databases. It will be used solely by the RUCDR as a secondary ID to help resolve labeling discrepancies that may occur during sample collection and submission.

6. RISKS AND DISCOMFORTS

The main potential risks (and burdens) to the subjects can be categorized as follows:

6.1. Risks of Discontinuing Medications for Study Participation

In order to participate in this study all subjects must be free of all antidepressant, antipsychotic, anxiolytic, anticonvulsant, mood stabilizing, muscle relaxant, centrally acting antihistaminergic, stimulant or insomnia medications (See Appendix 2) within 5 half-lives of baseline or at any time during after baseline and will have to remain off of all such medications other than study medication during the trial. There are risks associated with discontinuing medications which depend on the type of medication stopped, and the dosage and duration of use. Adverse effects requiring medical attention could also occur including seizures.

6.2. Risks of Being Without Therapy During the Study

During participation in this study subjects will go through periods of time without receiving treatment for their mood and anxiety spectrum disorder. This will occur because subjects will need to be off of all antidepressant and anxiolytic medications for 5 half-lives prior to starting the trial and during the trial, they may receive placebo during the study, the study medication may lack therapeutic effects for their condition, and all subjects will be off of study medications during weeks 8-12 of the study and will not be allowed to take other medications during this period. Risks of going without therapy include significant worsening of the symptoms of their mood and anxiety spectrum disorder.

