4. STUDY DESIGN AND METHODS

4.1. Study Overview

This study will be a six-site randomized, double-blind, PBO-controlled, parallel-group mono-therapy study to assess the effects of CERC-501 compared to PBO in adults age 21-65 years with mood and anxiety spectrum disorders. We will recruit a total of 90 subjects, of which 45 will be randomized to CERC-501 and 45 to placebo for 8 weeks of treatment.

Following phone screening subjects will come to the research unit/clinic for a face-toface screening visit. Subjects who sign informed consent will undergo rigorous screening including: a medical, psychiatric, medication, and treatment history, vital signs, physical examination, urine drug screen, MINI, clinical diagnostic interview for psychiatric disorders, beta-HCG serum pregnancy test (women), ECG, Snaith-Hamilton Pleasure Scale (SHAPS), Visual Analog Scale for Anhedonia, Temporal Experience of Pleasure Scale (TEPS), CSSRS, CGI-S, CGI-I and a battery of clinical laboratory tests (See Table 3 for Schedule of Assessments). All study events, their corresponding dates, and results of these examinations will be reported on the corresponding case report forms (CRFs). All subjects will be off of all antidepressant, antipsychotic, anxiolytic, anticonvulsant, mood stabilizing, muscle relaxant, centrally acting antihistaminergic, stimulant or insomnia medications (See Appendix 2) within 5 half-lives of baseline or at any time during after baseline and will have to remain off of all such medications other than study medication during the trial.

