Subjects who require tapering off of medications will discuss a medication tapering plan with a study physician. The study physician will develop a plan for safely decreasing and stopping medications that is tailored to each subject to minimize risks and discomfort and will be conducted in consultation with the subject's treating physician when applicable. This plan will be communicated to the subject including a detailed indication of the times at which medications are to be decreased, the possible side-effects that they may experience with decreases in medication dosage, the possible worsening of symptoms they may experience as medication dosage is lowered, and a plan for how to proceed if they develop side-effects or symptoms worsen. A study physician will be responsible for monitoring subjects during the washout including scheduling assessment visits if needed and addressing any side effects or worsening of symptoms that occur. Subjects who develop clinically significant adverse effects or worsening will receive appropriate assessment and care by a study physician which may include referral for evaluation/treatment. This plan will be designed so that subjects are free of all excluded medications at least 5 half-lives prior to the baseline visit (see Exclusion Criteria above). Subjects will also undergo a mock MRI scanning session at this visit.

Subjects will return to the research unit/clinic for a baseline assessment visit up to 30 days after the screening visit. At this visit subjects will undergo interval history, physical examination, ECG, vital signs, battery of laboratory tests, MRI, EEG, SHAPS, TEPS, VAS, CSSRS, PRT, EEfRT, HAM-D, HAM-A, CPFQ, CGI-I and CGI-S and will have the option of having blood collected to be sent to Rutgers for potential genetic analysis or other future analysis. Blood will also be collected for tests for assessment for gastric adverse events including gastrin and pepsinogen I/II levelsAt the end of this visit, subjects who continue to qualify will be randomized to CERC-501 10 mg or placebo in a 1:1 ratio using IVRS randomization within the EDC.

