The **Clinical Global Impression - Improvement** (CGI-I) is a widely administered clinician rated global measure of the degree of improvement from the initial assessment in subject overall illness severity. Subjects are rated on a 1-7 scale where 1 corresponds to "Very Much Improved", 2 is "Much Improved", the anchor for 3 is "Minimally Improved", the anchor for 4 is "No Change", 5 is "Minimally Worse", 6 is "Much Worse", and 7 is "Very Much Worse". It will be administered at all subject visits.

• During the course of the trial subjects for whom the CGI-I is greater than 5 will be removed from the study and appropriate care given, for safety purposes.

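### After study drug stops at Week 8, no contact is scheduled for 28 days while other medication is barred with no stated clinical-need exception; a Week 10 safety call and one clarifying exception would be a cheap improvement

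*Protocol*

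**What the plan says.** **Stopping study drug.** For the Week 8 visit, section 4.4 says that "study drug will be discontinued and subjects will be instructed to return to the clinic/research unit in 4 weeks". Table 3 has no column between Week 8 and Week 12, and the SAP study flow chart also goes straight from one to the other.

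**Medication in that period.** Section 6.2 states that "all subjects will be off of study medications during weeks 8-12 of the study and will not be allowed to take other medications" in that period. It continues: "Risks of going without therapy include significant worsening of the symptoms of their mood and anxiety spectrum disorder". Section 4.1 sets the trial-wide restriction on the listed psychotropic classes: subjects "will have to remain off of all such medications other than study medication during the trial". Neither section states an exception for clinical need.

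**Contact elsewhere.** The treatment visits are at Weeks 2, 4, 6 and 8. There is one telephone contact, at Week 1: "Subjects will be called after one week to assess for any safety concerns". Table 3 attaches the C-SSRS and PRISE to that call.

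**Care for worsening.** For the medication washout before baseline, section 4.1 requires a plan that is explained to the subject. It makes a study physician responsible for monitoring, with extra visits if needed, and adds: "Subjects who develop clinically significant adverse effects or worsening will receive appropriate assessment and care by a study physician". No matching text is written for Weeks 8-12.

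**The concern.** Subjects enter with a mood or anxiety disorder and anhedonia, and some will have tapered off earlier medication to take part. At Week 8 they stop study drug, stay off other treatment, and are next due to be seen four weeks later. The protocol itself expects that some may worsen significantly without therapy.

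What is at stake is how soon worsening is noticed and whether site staff and subjects know that needed treatment may start. The primary result is not at stake, because fMRI and the PRT end at Week 8.

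**Working it through.** The plan gives no figure to reproduce. The check is visit arithmetic, followed by a comparison of the safety rules.

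**1. Length of the gap.** Inputs: Week 8 = Day 56, Week 12 = Day 84, window ±4 days (Table 3 and section 4.4).

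- Nominal: 84 − 56 = 28 days.
- Both windows counted from baseline: (84 − 4) − (56 + 4) = 20 days to (84 + 4) − (56 − 4) = 36 days.
- Window counted from the actual Week 8 visit: 28 − 4 = 24 to 28 + 4 = 32 days.

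The SAP flow chart gives ±1 week for treatment visits. Using that at Week 8 and ±4 days at Week 12, the range is 17 to 39 days.

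**2. Comparison with other intervals.** Nominal gaps between scheduled contacts after randomization are 7, 7, 14, 14, 14 and 28 days (baseline, Week 1 call, Weeks 2, 4, 6, 8, 12). On-treatment visits 14 days apart can range from 14 − 8 = 6 to 14 + 8 = 22 days. The off-drug gap is 28/14 = 2 times the nominal on-treatment visit interval. Before randomization, screening to baseline can be up to 30 days, so this is the longest gap only after randomization.

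**3. What each existing rule needs between Week 8 and Week 12.**

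| Rule | What it needs | Scheduled chance to act before Week 12 |
|---|---|---|
| C-SSRS and psychiatrist review (7.1) | an assessment | none |
| CGI-I above 5 (7.2, 8.4.4.3) | a rating | none |
| Best-interest discontinuation (7.2) | the investigator's knowledge of the problem | none |
| Follow-up of adverse events (7.1, 16.2) | an event open at last dose, or a report | only for events already known |
| Withdrawal (4.5) | the subject's own decision | at any time, if the subject acts |

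All of these stay in force. None of them schedules a contact that would find new worsening before Week 12.

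**4. Effect of a Week 10 call.** The 28 days become 14 + 14, equal to the on-treatment interval. With ±4 days at each end, each half ranges from 6 to 22 days.

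**5. Timing against washout (an assumption; the conclusion does not depend on it).** The readable text gives no half-life. Assume linear one-compartment kinetics with once-daily dosing, and take the accumulation ratio R of 1.8 to 1.9 from section 1.2.3.2. Then R = 1/(1 − exp(−24k)).

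- R = 1.8: 24k = −ln(1 − 1/1.8) = 0.811; half-life = 24 × 0.693/0.811 = 20.5 h; five half-lives = 4.3 days.
- R = 1.9: 24k = 0.747; half-life = 22.3 h; five half-lives = 4.6 days.
- Upper end, from the stated time to steady state: 7 to 8 days.

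A call on day 14 falls after washout on either reading. At the 6-day window extreme it could fall just before the 7 to 8 day figure. This applies only to the CERC-501 arm.

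**The case against.** The strongest reply is that a route to care already exists in substance. The investigator can stop procedures in the subject's best interest, suicidality leads to psychiatrist review and intervention, removal comes with care, and anyone may withdraw. Section 6.2 is also a description of risk; the operative bar is exclusion criterion 6 with section 4.1, which cover listed drug classes. The protocol accepts an interval of similar length before baseline.

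Much of this stands, and it limits the point to timing of detection and clarity of wording. It does not remove it. Every route needs someone to know, and the pre-baseline interval has the physician monitoring plan that Weeks 8-12 lack.

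Three stronger readings are tempting, but the documents do not support them:

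- *Contact is least frequent in this period.* Screening to baseline may last up to 30 days with no fixed contact in Table 3.
- *Worsening is discovered only if the subject telephones.* The Week 12 visit includes the C-SSRS, SHAPS, CGI-S, CGI-I and PRISE, so worsening still present should be found there. Adverse events open at last dose are also followed. The supported claim is delay.
- *The CGI-I rule is defective because it misses relapse.* CGI-I is a clinician-rated "global measure of the degree of improvement from the initial assessment in subject overall illness severity", so a full return to the starting state scores 4. Section 8.4.4.3 says that "subjects for whom the CGI-I is greater than 5 will be removed from the study and appropriate care given, for safety purposes". That is a stop for subjects much worse than at entry, and a non-responder at 4 stays in the trial under the same rule during treatment. CGI-S, an absolute severity scale, is also collected at Week 12.

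Consent and contact pages are not visible. They may tell subjects whom to call.

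**Conclusion.** The point holds as a low-cost patient-safety improvement. After randomization, the longest interval without a scheduled contact falls just after study drug stops. In that interval section 6.2 bars other medication with no stated clinical-need exception. New worsening could go undetected for up to about four weeks (28 days nominal, up to 36 with the protocol windows).

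At most 90 subjects are concerned. The documents give no rate of worsening, so no number of affected subjects can be claimed. The conclusion rests on the visible schedule and assumes that the missing consent and contact pages add no scheduled contact.

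No primary or secondary aim in the visible text relies on Week 12: SAP section 1.2 sets the SHAPS comparison across 8 weeks of treatment. One uncertainty remains. Protocol section 9.1.2 does not say whether Week 12 SHAPS enters the repeated-measures model, and the SAP's analysis sections are not in the available text.

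**What to change.** 1. In Table 3 and section 4.4, repeat the Week 1 safety call at Week 10, ±4 days, with the C-SSRS and PRISE. Include the section 7.1 question on new symptoms or changes since the last visit. Its reference point is then Week 8.
2. In section 6.2, with a cross-reference in 4.1, state that the Weeks 8-12 restriction does not apply when the study physician judges treatment clinically necessary. Also state that the care described in 4.1 for worsening during washout applies in Weeks 8-12.
3. Flag Week 12 SHAPS, TEPS, VAS and CGI values taken after such treatment began, using the Treatment History that Table 3 already schedules at that visit.

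**Cost.** Up to 90 telephone calls, two sentences with matching consent text, and one data flag. Section 9.1.2 already plans to examine co-administration of psychotropic medications. The scientific cost is that some Week 12 clinical and safety values will be taken on outside treatment and be harder to interpret. The analysis plan should therefore say whether Week 12 SHAPS enters the model and, if so, how flagged values are handled. Sample size and the primary endpoint do not change.
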